6 STATISTICAL METHODS

No formal hypothesis testing will be conducted in this study. Data will be described mainly using descriptive statistics. Confidence intervals will be constructed to describe the precision of the point estimates of interest (e.g., objective response rate and disease control rate). Efficacy and safety analyses will be performed by dose escalation and dose expansion phases accordingly. Within dose escalation phase, data will be summarized by dose level within a dosing cohort or all combined. Within dose expansion phase, data will be summarized by cohort.

6.1 ANALYSIS POPULATIONS

- Safety Analysis Set (SAF): includes all patients enrolled into the study who receive any dose of pamiparib and/or TMZ. The Safety Analysis Set will be used for overall survival analysis and safety analyses.
- Efficacy-Evaluable Analysis Set: includes patients in the SAF who had evaluable disease in the dose escalation phase (or measurable disease in the dose expansion phase) at baseline and had at least one postbaseline tumor assessment unless discontinued treatment due to clinical progression or death prior to tumor assessment.

Evaluable disease means patients may have measurable (target lesions) or non-measurable lesions (non-target lesions); measurable disease means patients must have at least 1 measurable lesion (target lesions) and may or may not have non measurable lesions (non-target lesions).

- DLT Evaluable Analysis Set: includes patients who received $\geq 70\%$ of BGB-290 and TMZ during the DLT assessment window (Cycle 1). Additionally, patients who had a DLT event during the DLT assessment window despite receiving $< 70\%$ of the scheduled dose will also be included.
- PK Analysis Set: includes patients who received any dose of BGB-290 or TMZ, and contributed at least one plasma concentration.

6.2 DATA ANALYSIS GENERAL CONSIDERATIONS

6.2.1 Definitions and Computations

Study day: Study day will be calculated in reference to the date of the first combination treatment of BGB-290 and TMZ (e.g., Cycle 1 Day 1). For assessments conducted on or after the date of the first combination treatment, study day will be calculated as (assessment date – date of first dose of combination treatment + 1). For BGB-290 PK intensive group, BGB-290 is administered starting from 2 days prior to Cycle 1 Day 1 and noted as Study Day -2. For this group, study day will still be calculated from Cycle 1 Day 1 when both BGB-290 and TMZ are administered. There is no study day 0.

In the situation where the event date is partial or missing, the date will appear partial or missing in the listings. Study day and any corresponding durations will be presented based on the imputations specified in Appendix 10.1.

Treatment duration: The treatment duration will be calculated per different dosing scheme of BGB-290 and TMZ. Refer to Section 0for more detail.

Treatment-emergent period: The treatment-emergent period is defined as the period of time from the date of the first dose of either pamiparib or TMZ through 30 days after the last dose of pamiparib (permanent discontinuation of pamiparib) or initiation of new anti-cancer therapy. The treatment-emergent period will be used in the summaries of treatment-emergent adverse events (TEAEs) and concomitant medications.

TEAE: An AE started or worsened during the treatment-emergent period. Treatment-related SAEs occurred after treatment-emergent period will also be counted as TEAEs.

Baseline: Unless otherwise specified, a baseline value is defined as the last non-missing value collected before or on the date of first dose of any treatment.

All calculations and analyses will be conducted using SAS version 9.4 or higher.

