Grade 4 (PLT < 25 x 10 ⁹ /L)	Hold pamiparib and TMZ until resolved to Grade ≤ 1 or baseline and ↓ TMZ by 1 dose level
Renal	
Serum Creatinine	
2-3 x ULN	Hold BGB-290 and TMZ until resolved to Grade ≤1 or baseline 
 • If resolved ≤7 days, then maintain dose levels • If resolved >7 days, then ↓ TMZ by 1 dose level
Grade 3 (>3.0 - 6.0 x ULN) and Grade 4 (>6.0 x ULN)	Permanently discontinue pamiparib and TMZ
Hepatic	
Bilirubin	
Grade 2 (> 1.5 - 3.0 x ULN) and Grade 3 (> 3.0- 10.0 x ULN)	Hold pamiparib and TMZ until resolved to Grade ≤ 1 or baseline 
 • If resolved ≤ 7 days, then maintain dose levels • If resolved > 7 days, then ↓ pamiparib and TMZ by 1 dose level
Grade 4 (> 10.0 x ULN)	Permanently discontinue pamiparib and TMZ Note: If Grade 3 or 4 hyperbilirubinemia is due to the indirect (unconjugated) component only, and hemolysis as the etiology has been ruled out as per institutional guidelines (e.g. review of peripheral blood smear and haptoglobin determination), then ↓ pamiparib and TMZ by 1 dose level and continue study drug administration at the discretion of the investigator.
AST or ALT	
Grade 3 (> 5 and ≤ 20 x ULN)	Hold pamiparib and TMZ until AST and/or ALT resolved to ≤ 5 x ULN or baseline 
 • If ≤ 5 x ULN within 14 days, then ↓ pamiparib and TMZ by 1 dose level • If second episode, discontinue pamiparib and TMZ • If persistent for > 14 days, discontinue pamiparib and TMZ
Grade 4 (> 20 x ULN)	Permanently discontinue pamiparib and TMZ
Pancreatic	
Pancreatitis Grade 3 or 4	Permanently discontinue pamiparib and TMZ

Table 3: Criteria for Interruption and Modification of Pamiparib and Temozolomide Dosing (Continued)

Worst toxicity CTCAE 4.03 Grade (value)	Recommended dose modification any time during a cycle of therapy
Cardiac	
Cardiac - prolonged QTc interval QTcF > 500 ms or > 60 ms from the highest value at baseline or predose	
 • Obtain triplicate ECGs (5 minutes apart) ~1 hour after initial ECG • If mean QTcF > 500 ms, hold pamiparib and TMZ until evaluation of ECGs by cardiologist 
 a. Cardiology evaluation as soon as practical but within 7 days of initial abnormal ECG • If mean QTcF > 500 ms confirmed by cardiologist, discontinue pamiparib and TMZ
Cardiac general Grade 3	Hold pamiparib and TMZ until resolved to Grade ≤ 1 or baseline and ↓ TMZ 1 dose level

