7.5. Electrocardiogram

During screening, a single 12-lead ECG with assessment of PR interval, QRS duration, and QTc interval will be obtained within 14 days of Cycle 1 Day1. The screening ECG will be read locally to determine eligibility.

Dose Escalation and Expansion Cohorts 1-5 ONLY

During Cycle 1 and the pamiparib PK intensive period (Day -2), ECGs will be performed in triplicate on a machine provided by the sponsor within a 5-minute window **prior** to pamiparib PK assessments (see below and Section [7.8](#)) at the timepoints indicated below:

- Pre-dose (within 30 min prior to dose)
- Post-dose:

- 1 hour (\pm 15 min)
- 2 hours (\pm 30 min)
- 4 hours (\pm 30 min)
- 6 hours (\pm 30 min)

ECGs for each patient should be obtained from the same machine whenever possible. Central read of ECGs obtained during the PK assessments will be performed for dose escalation and dose expansion cohorts 1-5.

Locally obtained ECGs should be performed if clinically indicated for all patients enrolled in the study. To minimize postural variability, it is important that patients are resting and in a supine position for \geq 5 minutes prior to each ECG collection. Blood draws and other procedures should be avoided during the period immediately before ECG measurement, and activity should be controlled as much as possible to minimize variability because of the effects of physiologic stress.

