10. **For Dose Escalation and Dose Expansion Cohorts 1-5 Only:** ECGs will be performed in triplicate within a 5-minute window **prior** to Pamiparib PK assessments on Day -2 or Days 1 and 15. ECGs collected on the days of PK assessment will be performed on a machine provided by the sponsor and will be sent to a central reader. The same machine should be used for each patient whenever possible.
11. Hematology includes hemoglobin, platelet count, white blood cell count, neutrophil count, and lymphocyte count. Chemistry includes albumin, alkaline phosphatase, alanine aminotransferase, aspartate aminotransferase, blood urea nitrogen, chloride, creatinine, glucose, lactate dehydrogenase, phosphate, potassium, sodium, total bilirubin, and total protein.
Urinalysis includes blood, glucose, ketones, protein, red blood cells, and white blood cells.
In the event of clinically significant laboratory results, such as neutropenia (absolute neutrophil count $< 1000/\text{mm}^3$), thrombocytopenia (platelets $< 50,000/\text{mm}^3$), or Grade ≥ 3 clinical chemistry toxicity (per NCI CTCAE v4.03), these assessments will be conducted as frequently as the investigator feels is necessary until toxicity resolves to Grade ≤ 2 .
12. Screening blood and urine tests must be performed within 14 days of Day 1. If they were performed within 4 days of Day 1 they do not need to be repeated on Cycle 1 Day 1.
13. If urine protein is $\geq 2+$ by dipstick, a 24-hour urine for total protein and a random urine for total protein and creatinine will be obtained and evaluated (Section 7.6.3).
14. Only in women of childbearing potential; a serum pregnancy test must be taken ≤ 7 days from Cycle 1, Day 1.
15. For subsequent pregnancy testing on study and at EOT, urine pregnancy tests are allowed. If a urine pregnancy test is positive, a confirmatory serum pregnancy test is required.
16. A computed tomography (CT) or MRI scan of the thorax, abdomen, and pelvis plus other relevant evaluations as appropriate will be performed once every 8 weeks ± 7 days to assess all known disease. A CT/MRI taken within 28 days (Screening Period) of Cycle 1 Day 1 does not need to be re-taken. Patients without PD at the EOT Visit should be followed with tumor assessments every 12 weeks (± 7 days).

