Vital signs (including weight)	X						X	X	X
ECOG performance status	X								
Hematology	X								
Clinical chemistry	X								
Coagulation	X								
Urinalysis ⁴	X								
Blood sample collection for biomarkers ⁵	X								
Computed tomography or MRI ⁶	X								
Triplicate ECGs ⁷	X			X	X	X	X		
Pamiparib PK assessments ⁸	X		X	X	X	X	X	X	X
Pamiparib Dosing ⁹		X							X
Archival Tumor Tissues ¹⁰	X								
Fresh Tumor Tissues ¹¹ (additional consent required)	X								
Adverse events	X							X	X
TMZ Dosing ¹²									X
TMZ PK assessments ¹³									X

CT: Computerized tomography; ECG: electrocardiogram; ECOG: Eastern Cooperative Oncology Group; MRI: magnetic resonance imaging; PK: pharmacokinetic;

TMZ: Temozolomide; X: to be performed.

Notes: All assessments except for post-dose ECGs and PK samples and biopsies must occur before pamiparib administration. ECGs must occur before PK sampling and biopsies must be performed after all ECGs have been completed on Day -2. For patients enrolled into the PK intensive part of the study, the pre-dose biopsy must occur **after** the patient was approved for enrollment and **before** dosing on Cycle 1 Day -2.

1. Screening must occur within 28 days of Day -2. Assessments obtained within 4 days of Day -2 do not have to be repeated on Day -2. Patient registration may occur as late as Day -2 prior to any study treatment.
2. Complete physical examination includes the following items: 1) general appearance; 2) head, eyes, ears, nose, and throat; 3) neck; 4) heart; 5) chest (including lungs); 6) abdomen; 7) extremities; 8) skin; 9) lymph nodes; 10) cardio-vascular; 11) neurological status.
3. A limited physical examination should be directed at the evaluation of symptoms or specific safety issues. Changes from baseline abnormalities should be recorded at each subsequent physical examination. New or worsening abnormalities should be recorded as AEs if appropriate.
4. If urine protein is $\geq 2+$ by dipstick, a 24-hour urine for total protein and a random urine for total protein and creatinine will be obtained and evaluated (Section 7.6.3).
5. Blood samples will be collected **before** study treatment on Day -2 for the assessment of germline *BRCA* and/or other mutation analysis (8 ml). In addition, two blood samples (10 mL each) must be collected for plasma markers (e.g., CNA), TMZ treatment, and PARP inhibition. Instructions for the processing, storage, and shipping of samples will be provided in the Study Manual.

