8 CHANGES IN THE PLANNED ANALYSIS

There are some changes in the planned analysis and they are listed below:

- DLT will be provided in a listing and no descriptive statistics will be provided.
- Subgroup analysis for ORR will only be done for SCLC patients in chemosensitivity and number of prior regimens.
- All by-visit analyses will be removed, and the following will be performed: hematology data will be presented in a shift table and serum chemistry will be provided in a listing. ECG will be listed. A listing of QTcF will be provided for patients with abnormal postbaseline values and abnormal changes from baseline. ECOG and vital signs will be provided in listings.
- Ninety percent CIs will be presented instead of 95% CIs.
- OS analyses will be conducted in SAF instead of Efficacy Evaluable Analysis Set. Only PFS and OS analyses will be conducted and not PFS-6m and OS-6m analyses.
- Efficacy analyses such as ORR, PFS and DOR will be based on radiographic responses or radiographic progression.
- Treatment-emergent SAEs, treatment-related TEAEs, TEAEs with grade 3 or above, and treatment-related SAEs will be summarized by SOC, PT and CTCAE grade. AEs that led

to death and AEs that led to treatment discontinuation, dose reduction or dose interruption will only be listed.

- Number of treatment cycles will not be summarized. Instead, reasons for dose reduction, dose interruption and missed dose will be summarized.

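### The SAP's date-only baseline rule makes a post-dose ECG the QTcF baseline in dose escalation and Cohorts 1-5, which distorts the change-based QTcF listing

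*SAP*

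**What the plan says.** SAP 6.2.1 sets a general rule that applies unless another is specified: "a baseline value is defined as the last non-missing value collected before or on the date of first dose of any treatment". The condition is a calendar date. Neither SAP 6.4.6 (Electrocardiograms) nor SAP Section 8 gives a different baseline for ECG.

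Protocol 7.5, for dose escalation and Cohorts 1-5, states: "During Cycle 1 and the pamiparib PK intensive period (Day -2), ECGs will be performed in triplicate on a machine provided by the sponsor". It lists a pre-dose time point and post-dose time points at 1, 2, 4 and 6 h. Footnote 10 to Appendix 1 Table 1 ties the triplicates to "Pamiparib PK assessments on Day -2 or Days 1 and 15". Appendix 1 Table 2 marks them pre-dose and at 1, 2, 4 and 6 h on Day -2, and its note confirms that later readings are intended: "All assessments except for post-dose ECGs and PK samples and biopsies must occur before pamiparib administration".

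The output that uses the baseline is in SAP Section 8: "A listing of QTcF will be provided for patients with abnormal postbaseline values and abnormal changes from baseline".

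**The concern.** Baseline should describe the patient before exposure. Under a date-only rule, any measure repeated after dosing on the first-dose day takes its baseline from an exposed patient. ECG is the measure where this matters, because the protocol deliberately schedules same-day post-dose recordings to look for an effect on QTcF.

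Two things go wrong in the Section 8 listing. Every later change is measured from a post-dose reference, and the first-day post-dose recordings no longer follow baseline. Protocol 11.3.6 had planned descriptive statistics for ECG changes from baseline. SAP Section 8 replaces them with listings, so this listing is the one ECG output named in the SAP that is based on change.

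**Working it through.** The documents give no figure to reproduce. The check applies the rule to the schedule and then illustrates the size.

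**Step 1: which date is the first dose of any treatment?**
- PK-intensive patients (the first 15 in Protocol 7.8.1, about 20 in Protocol 8.3.1): Day -2, when pamiparib is given alone.
- All others: Cycle 1 Day 1.

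**Step 2: which ECGs fall on that date, and which is last?**

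| Group | Scheduled that day | Baseline under SAP 6.2.1 | Post-dose time points not postbaseline |
|---|---|---|---|
| PK-intensive, Day -2 | pre-dose, 1, 2, 4, 6 h | 6 h | 4 of 4 |
| Other escalation and Cohorts 1-5, Day 1, per Protocol 7.5 | pre-dose, 1, 2, 4, 6 h | 6 h | 4 of 4 |
| Same patients, if ECGs follow the sparse PK times (Protocol 7.8.1) | pre-dose, 1, 2, 4 h | 4 h | 3 of 3 |
| Cohort 6 | no scheduled triplicates | screening ECG | none |

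SAP 6.2.1 does not define postbaseline, so I take it to mean after the baseline value. If it were programmed as after first dose, first-day ECGs would count, but their change would still be measured from the last of them.

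If the 'or' in footnote 10 means that PK-intensive patients have triplicates on Day -2 only, they would have no scheduled triplicate left after baseline.

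**Step 3: how does the change move?** Let P be pre-dose QTcF, L the last first-day value and D the Day 15 value.

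SAP change = D − L = (D − P) − (L − P)

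The reported change is therefore short by L − P, the first-day effect at the last ECG.

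Invented values: P = 420, L = 450, D = 490 ms.
- Against pre-dose: 490 − 420 = +70 ms.
- Under the SAP rule: 490 − 450 = +40 ms, short by 450 − 420 = 30 ms.

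**Step 4: order of magnitude, under assumptions.** The model is one-compartment, oral and twice daily, with a QTcF effect proportional to concentration, scaled so that the Day 15 peak effect is +60 ms. The half-life is 13 h (range 5.4 to 34 h, Protocol 1.5.1). Absorption rates of 0.7, 1.5 and 3 per h are assumed.

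- Single dose: c(t) = ka/(ka − k) × [exp(−kt) − exp(−ka·t)], with k = ln 2 / half-life. Day 15 is the sum of c over 28 doses 12 h apart.
- Check on the model: accumulation = 1/(1 − exp(−12 ln 2 / 13)) = 2.12, consistent with the roughly 2-fold figure in Protocol 1.5.1.
- Example (13 h, ka = 1.5): the first-day effect at 6 h is 23.5 ms, so +60 is reported as 60 − 23.5 = +36.5 ms.

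| Baseline taken at | Half-life 13 h | Half-life 5.4 to 34 h |
|---|---|---|
| 6 h | +34 to +38 ms | +24 to +48 ms |
| 4 h | +33 to +35 ms | +16 to +48 ms |

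In the same model at 13 h, the first-day peak is about +27 to +28 ms against pre-dose. Under the literal rule no first-day change is reported.

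**The case against.** The strongest reply is that little is lost. SAP 6.4.6 also lists ECG findings by visit or time point, and abnormal QTcF from the triplicates with no change criterion, so pre-dose and later values can still be read side by side. The study has no QT endpoint and no formal test. Both points stand, and they confine the problem to one listing.

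A reader might infer that patients above a 60 ms increase would go unreported. The documents do not support that. The 60 ms figure is the on-study trigger in Protocol Table 3, which has its own reference, "from the highest value at baseline or predose". The SAP sets no threshold for an abnormal value or change. It is also unclear whether the 'and' in its listing rule requires both conditions or either; if either is enough, an abnormal absolute value in a later ECG is listed whatever the baseline.

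A reader might also infer that the listing is certain to be biased toward no change. That requires a QTcF effect. Protocol 1.4.1.1 reports no apparent hERG inhibition and no QT prolongation in dogs. Without an effect, the post-dose reference is still wrong but the error has no predictable direction.

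It may be said that everyone reads baseline as pre-dose. The protocol does: Section 8.3.1 puts baseline assessments before dosing on Day -2, and Section 11.3.3 equates baseline with pretreatment. The SAP wording departs from this, and programmers work from the SAP. The general statement in Protocol 8.3.2 that Cycle 1 assessments precede dosing does not cancel the post-dose ECGs that Section 7.5 schedules.

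**Conclusion.** The point holds within limits. As written, SAP 6.2.1 makes the last post-dose ECG of the first-dose day the QTcF baseline in dose escalation and Cohorts 1-5. It also removes three or four first-day post-dose time points per patient from the postbaseline set. The change-from-baseline and postbaseline parts of the SAP Section 8 QTcF listing are then wrong.

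The understatement equals the QTcF effect at that last ECG. The figures above rest on invented values, assumed absorption rates and an assumed linear effect, and they are not evidence that pamiparib prolongs QT.

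Absolute values stay visible, and the on-study QTcF trigger is untouched. Cohort 6 has no scheduled first-day triplicates. Laboratory samples are drawn before dosing (Protocol 7.6). Vital signs, although marked at 6 h on Day -2, are only listed, so no planned result moves. This is worth correcting before programming because it concerns a safety output, but it does not reach a primary endpoint.

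**What to change.** In SAP 6.2.1, define baseline as the last non-missing value before the first dose of any study drug. In SAP 6.4.6, add that QTcF baseline is the scheduled pre-dose assessment on the first-dose date, with the screening ECG as fallback, and that all post-dose ECGs on that date are postbaseline. State how the triplicate is reduced to one value. The mean of the pre-dose triplicate is one reasonable choice; it need not match the highest-value reference in Protocol Table 3, which serves another purpose.

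The documents do not show that ECG clock times are recorded. Where no time exists, use the nominal pre-dose or post-dose label from Protocol 7.5.

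While editing, state whether the Section 8 listing needs both conditions or either, and what counts as abnormal.

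The baseline correction costs one SAP sentence and minor programming. It needs no new data, because the pre-dose ECG is already scheduled.

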6.2.2 Conventions

Unless otherwise specified, the following conventions will be applied to all analyses:

- 1 year = 365.25 days. Number of years is calculated as (days/365.25) rounded up to 1 decimal place.
- 1 month = 30.4375 days. Number of months is calculated as (days/30.4375) rounded up to 1 decimal place.
- P-values will be rounded to 4 decimal places. P-values that round to 0.0000 will be presented as '< 0.0001' and p-values that round to 1.000 will be presented as '> 0.9999'.
- Duration of imaging-based event endpoints (such as PFS) will be based on the actual date the radiograph was obtained rather than the associated visit date.
- Missing efficacy or safety data will not be imputed unless otherwise specified.
- For laboratory results collected as < or >, a numeric value, 0.0000000001 will be subtracted or added, respectively, to the value.
- For by-visit observed data analyses, percentages will be calculated based on the number of patients with nonmissing data as the denominator, unless otherwise specified.
- For continuous endpoints, summary statistics will include n, mean, standard deviation, median, Q1, Q3 and range (minimum and maximum). For PK analysis, both geometric mean and geometric CV will be included.
- For discrete endpoints, summary statistics will include frequencies and percentages.

6.2.3 Handling of Missing Data

Missing data will not be imputed unless otherwise specified elsewhere in the SAP. Missing dates or partially missing dates will be imputed conservatively for adverse events and

prior/concomitant medications/procedures. Specific rules for handling of missing or partially missing dates for adverse events and prior/concomitant medications/procedures are provided in Appendix 10.1.

By-visit endpoints will be analyzed using observed data, unless otherwise specified. For observed data analyses, missing data will not be imputed and only the observed records will be included.

When summarizing categorical variables, patients with missing data are included in the denominator to calculate percentages unless otherwise specified. When needed, the category of “Missing” is created and the number of patients with missing data is presented.

When summarizing continuous variables, patients with missing data are not included in calculations. No imputations are made.

